9.3.4 Vital Signs and Body Weight

The following vital signs (blood pressure, pulse rate, body temperature) and body weight will be tabulated at each time point.

- Descriptive statistics of the measured values
- Descriptive statistics of the change from baseline

9.3.5 ECG (12-Lead ECG)

Electrocardiographic (ECG) assessment by site investigator will be used for the analysis.

The following items will be tabulated for heart rate, PR interval, RR interval, QRS interval, QT interval, and QT interval as corrected by Fridericia's formula (QTcF interval) at each time point.

- Descriptive statistics of the measured values
- Descriptive statistics of the change from baseline

The number of subjects and incidence of the following items will be tabulated by cohort for QTcF interval of last value and worst value (maximum value obtained after the start of IMP administration).

- Measured values will be classified as "greater than 450 ms", "greater than 480 ms", and "greater than 500 ms" for tabulation.
- Changes from baseline will be classified as "greater than 30 ms" and "greater than 60 ms" for tabulation.

The following item will be tabulated by cohort using the normality judgment (normal or abnormal) for the electrocardiogram at each time point.

- Shift table from baseline

9.3.6 ECOG PS

The following item will be tabulated for the ECOG PS at each time point.

- Frequency distribution of each ECOG PS score

9.3.7 Chest X-ray

The following item will be tabulated using the normality judgment (normal or abnormal) for the chest x-ray at each time point.

- Shift table from baseline

10 Efficacy Analysis

The efficacy analysis set will be used in efficacy analyses. The following analyses will be performed by cohort and overall (Cohorts 1, 2, and 4).

10.1 Complete Remission Rate, Composite Complete Remission Rate, Overall Remission Rate

The following analysis will be conducted by cohort and overall (Cohorts 1, 2, and 4).

- Distribution of remission in each course [CR, CRp, CRi, PR No response, progressive disease, and not evaluable (NE)]
- Distribution of the best overall remission: complete remission rate (CR), composite complete remission rate (CR + CRp + CRi), overall remission rate (CR + CRp + CRi + PR)

10.2 Duration of Composite Complete Remission

The following analysis will be conducted by cohort and overall (Cohorts 1, 2, and 4) for the subjects with composite complete remission.

- Summary of duration of composite complete remission using descriptive statistics.

10.3 Overall Survival

The following analysis will be conducted by cohort and overall (Cohorts 1, 2, and 4) in the efficacy analysis set. Also, same analysis will be conducted for responders, non-responders, and overall in efficacy analysis set. Responders will be defined as those subjects who meet the criteria of overall remission.

- Kaplan–Meier plots with median survival time

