##### **1.2.2.1.1.1 SGI-110-01 Phase 1 Dose Escalation Segment (AML/MDS; Monotherapy)**

As of 26 Jul 2013, enrollment in the dose escalation segment has been completed, and treatment is ongoing.

The subjects enrolled in this segment had relapsed or refractory intermediate- or high-risk MDS (including chronic myelomonocytic leukemia [CMML]) or AML. The dose was escalated based on PK (area under the curve [AUC] for decitabine; see [Section 1.2.2.1.2](#)) and pharmacodynamic (PD) (hypomethylation in LINE-1; see [Section 1.2.2.1.3](#)) evaluations. Each cycle consisted of 28 days. The subjects were randomized to receive SGI-110 once daily for 5 days or once weekly for 3 weeks. Randomization to these two regimens was completed, and the study plan was modified to enroll subjects to receive SGI-110 twice weekly for 3 weeks (initial dose, 60 mg/m^2) because data of hypomethylation in LINE-1 showed that the 3-week once-weekly regimen was inferior.

The primary endpoint in this segment was to determine the BED and MTD. The MTD was decided based on the incidence of dose-limiting toxicities (DLTs) in Cycle 1. The safety profiles, PK profiles, and remission rates (hematological improvement and response duration) for SGI-110 and decitabine, and time to progression to AML (only in subjects with MDS) were also evaluated.

In the study database as of 26 Jul 2013, data from a total of 94 subjects in the dose escalation segment are available for analyses. SGI-110 was administered SC to 93 subjects (one subject was randomized to the 90 mg/m^2 once-weekly group but did not receive SGI-110). Of these, SGI-110 was administered to 44 subjects once daily for 5 days (3 to 125 mg/m^2), 34 subjects once weekly for 3 weeks (6 to 125 mg/m^2), and 15 subjects twice weekly for 3 weeks (60 or 90 mg/m^2).

SGI-110 was administered SC to the majority of subjects (67%) for 2 cycles. SGI-110 was administered SC to 46%, 28%, 18%, and 14% of the subjects for 3, 4, 5, and 6 cycles, respectively. The actual number of cycles was similar among the regimens.

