#### **1.2.2.1.1.2 SGI-110-01 Phase 2 Dose Expansion Segment (AML/MDS; Monotherapy)**

As of 26 Jul 2013, enrollment in the dose expansion segment is ongoing.

This segment was implemented as a phase 2 randomized, extension study and evaluated subjects with the following four diseases:

- Relapsed or refractory AML
- Relapsed intermediate-2 or high-risk MDS (including CMML) previously treated with a hypomethylating agent
- Treatment-naïve AML in elderly subjects (aged 65 years or older)
- Treatment-naïve MDS (including CMML)

In the study, the subjects were randomized to receive either 60 or 90 mg/m^2 once daily for 5 days (one dose a day 5 times). Thereafter, the protocol was revised to add a fifth treatment group, consisting of non-randomized subjects receiving 60 mg/m^2 once daily for 10 days (subjects with relapsed or refractory AML only).

The primary endpoint of the phase 2 study was an overall remission rate (CR, CRp, and CRi) assessed using criteria of an international working group. A PD action for DNA methylation in LINE-1 was also evaluated.

In the study database as of 26 Jul 2013, data from a total of 109 subjects in the phase 2 dose expansion segment are available for analyses. SGI-110 was administered to 108 subjects (one subject was randomized but did not receive SGI-110).

Overall, SGI-110 was administered SC in the majority of subjects (78%) for 2 cycles. SGI-110 was administered SC to 51%, 31%, 19%, and 10% of the subjects for 3, 4, 5, and 6 cycles, respectively.

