- iBody weight will be measured and the dose of IMP to be administered will be determined according to the calculation of BSA.
- jCardiac function (echocardiography or multiple-gated acquisition [MUGA] scan) or respiratory function (DLCO or FEV 1) will be measured.
- kHemoglobin (Hb), hematocrit (Hct), RBC, WBC, differential WBC (visual count: blast cells [leukemia cells], lymphoblastoid cells, monoblasts, promyelocytes, myelocytes, metamyelocytes, segmented neutrophils, stab leucocytes, lymphocytes, eosinophils, monocytes, basophils, prolymphocytes, promonocytes), platelet count, reticulocytes
- lAST (glutamate oxaloacetate transaminase [GOT]), ALT (glutamate pyruvate transaminase [GPT]), alkaline phosphatase (ALP), lactate dehydrogenase (LDH), total protein (TP), albumin (ALB), T-Bil, blood urea nitrogen (BUN), uric acid (UA), Cr, blood glucose (fasting), Ca, Mg, Na, K, Cl
- mBilirubin, occult blood, protein, urobilinogen
- nBone marrow aspiration will be performed at screening and on Day 29 of Course 1. In Course 2 and subsequent courses, if peripheral blood testing indicates that the subject meets criteria for remission, or if clear disease progression is observed, bone marrow aspiration will be performed and the following items will be examined: percentage of bone marrow fluid (blasts, lymphoblasts, monoblasts, promyelocytes, myelocytes, metamyelocytes, segmented neutrophils, stab leucocytes, lymphocytes, eosinophils, monocytes, basophils, normoblasts, pronormoblasts, erythroblasts, plasma cells, and megakaryocytes), myeloid/erythroid ratio (M/E ratio), cellularity.  
(If bone marrow aspiration has already been performed and any of the above items have been measured prior to acquisition of written informed consent and within the acceptable time window for the screening period [within 28 days before commencement of IMP administration], then those results can be used as the screening data, provided the subject's consent is obtained.)
- oBlood sampling for PK:  
Day 1 and Day 5: predose, 15 minutes, 30 minutes, 60 minutes, 90 minutes, 2 hours, 3 hours, 4 hours, 6 hours, 8 hours, 24 hours after dosing  
Day 2 (24 hours after Day 1 dosing), Day 3, and Day 4: predose (predose on Day 2 is the same as 24 hours postdose on Day 1)  
[Acceptable time windows]
- |                     |   |   |
|---------------------|---|---|

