5.1.2 Efficacy Analysis Set

The efficacy analysis set will include subjects who have received at least one dose of the IMP and have data of the efficacy endpoints after the start of IMP administration.

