6.2.7 Overall Survival

Overall survival is defined as the number of days from the day the subject received the first dose of IMP to the date of death (regardless of cause).

Survival time will be censored on the last date of survival confirmation if a subject is alive or lost to follow-up.

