10.5 Subgroup Analysis

No subgroup analysis will be conducted, since the number of subjects in this study will be very limited.

11 Pharmacodynamic Analysis

The PD analysis set will be used for pharmacodynamics analyses. The following analyses will be performed by cohort and overall (Cohorts 1, 2, and 4).

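### SAP 10.3 compares survival from first dose by ever-response, which favours responders on average even if response has no effect on survival

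*SAP*

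**What the plan says.** SAP 6.2.7 sets the time origin: "Overall survival is defined as the number of days from the day the subject received the first dose of IMP to the date of death". SAP 10.3 asks for Kaplan-Meier plots with median survival by cohort and for Cohorts 1, 2 and 4 together, and then extends this: "Also, same analysis will be conducted for responders, non-responders, and overall in efficacy analysis set". The grouping rule is "Responders will be defined as those subjects who meet the criteria of overall remission", which under SAP 6.2.5 means CR, CRp, CRi or PR. No time limit is placed on when the response must occur.

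On assessment times, the schedule footnotes in Protocol 7.1 state: "Bone marrow aspiration will be performed at screening and on Day 29 of Course 1". From Course 2 onward, marrow and efficacy assessments are triggered by blood findings that suggest remission or by clear progression, so responder status can be gained in any later course. A withdrawal marrow could fall slightly before Day 29.

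SAP 10.5 says: "No subgroup analysis will be conducted, since the number of subjects in this study will be very limited". SAP 6.5 rules out tests and interval estimates. Protocol 11.3.2 plans only a Kaplan-Meier plot for each cohort with at least 6 treated subjects. The responder split appears only in the SAP, and SAP section 13, which lists changes from the protocol's analyses, does not mention it.

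**The concern.** The groups are defined by something that happens after the survival clock has started. To enter the responder curve a subject must survive to a response assessment, about four weeks at the earliest and up to several months for later responses. A subject who dies before that can only be a non-responder. This is immortal-time bias, and its direction follows from the definitions alone, whatever the survival distribution.

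At stake is how a planned secondary display will be read. Two curves with two medians invite the reader to conclude that remission prolonged survival. The SAP gives no landmark, no time-dependent version and no caution, and with no intervals planned nothing on the figure shows how imprecise it is. The rationale in SAP 10.5 for avoiding subgroups, very small numbers, applies equally to this split.

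**Working it through.** **No figure to reproduce.** The plan states no survival assumption, and the documents give no overall survival figure for this trial or the preceding study. The size has to be found under stated assumptions.

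**Inputs from the documents**
- Clock from first dose (SAP 6.2.7); responder means ever meeting overall remission (SAP 10.3).
- Courses of 28 days, so assessments fall 28, 56, 84 and 112 days after first dose. Day 29 of Course 1 is 28 days after a first dose on Day 1.
- Share of subjects receiving Courses 2, 3 and 4 in the preceding study: 67%, 46% and 28% in the dose-escalation segment (Protocol 1.2.2.1.1.1: "SGI-110 was administered SC to 46%, 28%, 18%, and 14% of the subjects for 3, 4, 5, and 6 cycles, respectively") and 78%, 51% and 31% in the dose-expansion segment (Protocol 1.2.2.1.1.2: "SGI-110 was administered SC to 51%, 31%, 19%, and 10% of the subjects for 3, 4, 5, and 6 cycles, respectively"). Both are interim with treatment ongoing, so they may be low.
- At most 24 subjects, of whom at most 18 are in Cohorts 1, 2 and 4 (Protocol 3.4).

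**Assumptions**
- Exponential survival with median 180 days (90 and 270 also run).
- Response independent of remaining survival, i.e. no true effect.
- No censoring.
- Response probability 20% if all responses fall at Day 28, otherwise 10% per course.

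**Closed form for the two extreme scenarios at 180 days.** Let S(t) = 2^(−t/180), so S(28) = 0.898, S(56) = 0.806, S(84) = 0.724 and S(112) = 0.650.

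*All responses at Day 28, probability 20%.*
- Responder median = 28 + 180 = 208 days.
- Non-responders are 1 − 0.2 × 0.898 = 0.820 of all subjects. Their median solves 0.8 × S(m) = 0.820/2, so S(m) = 0.513 and m = 173 days.
- Ratio 208/173 = 1.20.

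*10% per course among all survivors through Course 4.*
- Responders = 0.1 × 0.898 + 0.09 × 0.806 + 0.081 × 0.724 + 0.0729 × 0.650 = 0.268.
- The weights sum to 0.3439. The responder median solves 0.3439 × S(m) = 0.268/2, giving 244 days.
- The non-responder median solves 0.6561 × S(m) = 0.732/2, giving 152 days.
- Ratio 1.61.

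**Simulation, 2,000,000 subjects per scenario** (responder / non-responder median in days):

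| Scenario | Median 90 | Median 180 | Median 270 |
|---|---|---|---|
| All responses at Day 28 | 118 / 84 | 209 / 173 (+20%) | 298 / 264 |
| 10% per course, escalation-segment retention | 146 / 76 | 235 / 165 (+43%) | 324 / 255 |
| 10% per course, expansion-segment retention | 147 / 75 | 236 / 163 (+45%) | 324 / 253 |
| 10% per course, all survivors | 153 / 71 | 244 / 152 (+61%) | 336 / 239 |

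The excess is 41–114% at 90 days and 13–40% at 270 days. At 180 days, varying response from 5% to 20% per course gives 37–57% with escalation-segment retention and 38–64% with expansion-segment retention.

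**Different response model.** A separate calculation used overall response rates reported for the preceding study (Protocol 1.2.2.1.1.2 and 6.1), again at 180 days. With timing running from all responses at Day 29 to responses spread over Courses 1–4, the excess is 19–48% at a 16% rate, 22–56% at 25%, and 39–109% at 53%.

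**Reading of the efficacy set.** SAP 5.1.2 requires that subjects "have data of the efficacy endpoints after the start of IMP administration". If deaths before Day 28 are dropped on that basis, the medians at 180 days become 209/208, 235/200, 236/199 and 245/191, an excess of 0–28%.

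**Single trials.** In 40,000 simulated null trials at 180 days without censoring, the responder median is ahead in 62%, 73%, 73% and 79% for 18 subjects and in 63%, 74%, 75% and 82% for 24. About 50% would be expected without bias.

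**Check of the remedy.** With status fixed and the clock started at Day 28 or Day 56, the medians are 179–181 against 180 days in every scenario. Restricting to Day 29 survivors while still counting later responses does not suffice: an excess of 23–27% remains at response rates of 16–25% spread over Courses 1–4.

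**The case against.** The strongest reply is that little hangs on this figure. It is secondary and descriptive, no test or interval is planned, nothing in the documents says it will support a claim that remission prolongs survival, and the DLT endpoint and the cohort curves are unaffected. That stands, and it limits the severity. It does not make the display a fair comparison, and more subjects would not remove the bias.

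The size is also open to challenge. It rests on an assumed median and on assumed response rate and timing, and the retention figures pool AML with MDS and include regimens not used here. With an assumed 200–600-day censoring time, single-trial shares fall: for all responses at Day 28, responders are ahead in about 53% of trials of 18 and 56% of trials of 24 where both medians are estimable. At that low end one realised plot is barely distinguishable from chance. With responses among all survivors through Course 4, the shares fall less, to 74% and 79%. These points change the size and not the direction.

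Non-responders are not defined, and subjects without a marrow examination are recorded as not evaluable (Protocol 7.2.3.1). If they were left out, the gap would shrink towards the 0–28% range. The natural reading is the complement of responders. Since overall survival is itself an efficacy endpoint, early deaths normally stay in the set.

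Finally, SAP 10.5 may be meant for subgroups by patient characteristics, and SAP 11.1 uses the same split for LINE-1 plots. So 10.3 need not contradict 10.5. The bias does not depend on that point.

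**Conclusion.** The concern holds. As written, the responder versus non-responder survival display is biased towards longer responder survival on average, and nothing else in the SAP or protocol corrects it. The direction rests only on the SAP's definitions. The size, about 20–60% longer median survival under no effect, rests on an assumed 180-day exponential median, overall response of roughly 16–25% or 10% per course, responses between the end of Course 1 and Course 4, and early deaths kept in the efficacy set. It is larger with shorter survival, higher response rates or later responses. It is smaller with longer survival, and can reach zero if early deaths are excluded and all responses come at the first assessment. With at most 24 subjects a single trial may show no gap. The plan should be changed, but the consequence is confined to the interpretation of one descriptive figure.

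**What to change.** In SAP 10.3, do not present first-dose Kaplan-Meier curves and medians by ever-response. Keep the first-dose curves by cohort and overall.

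- **Cheapest:** delete the split. The protocol did not plan it, and deletion fits the small-numbers reasoning in SAP 10.5.
- **If a comparison is wanted:** either show response as time-dependent (Simon-Makuch plot), or pre-state a landmark at the end of Course 2, with Day 29 of Course 1 as a sensitivity. Fix response status at the landmark, start the clock there, and include only subjects alive and in follow-up.
- **In either case:** pre-state a minimum number of responders, for example 3. Below it, drop the comparison and list individual response and survival dates.

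A sentence stating that the plot cannot show an effect of response on survival would be better than nothing, but it leaves the biased medians in place.

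The cost is SAP wording and one deleted or re-programmed figure. A landmark has real drawbacks: early deaths leave the figure (about 19% of subjects by Day 56 at a 180-day median, from 1 − 0.806), later responses count as non-response, and the comparison is still not causal. Responders will be few. At 10% per course with the documented retention and a 180-day median, a Day 28 landmark leaves about 1.6 responders of 18 or 2.1 of 24, with one or none in 51% or 36% of trials. The end of Course 2 leaves about 2.4–2.6 or 3.2–3.4, with one or none in 25–28% or 12–15%. Those numbers favour deletion.

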10.4 Adjustment for Covariates

No adjustment for covariates will be considered, since statistical tests and interval estimations will not be performed.

10.5 Subgroup Analysis

No subgroup analysis will be conducted, since the number of subjects in this study will be very limited.

11 Pharmacodynamic Analysis

The PD analysis set will be used for pharmacodynamics analyses. The following analyses will be performed by cohort and overall (Cohorts 1, 2, and 4).

11.1 DNA Methylation Inhibition

The following analysis will be conducted by cohort and overall (Cohorts 1, 2, and 4) for the subjects with the measurement of the degree of DNA methylation inhibition of LINE-1.

- Descriptive statistics of the DNA LINE-1 demethylation (defined as percent change from baseline in methylation value) at each time point. Also, line plots will be used to assess DNA LINE-1 demethylation [Mean \pm Standard deviation (SD)] at each time point.
- Summary of the maximum DNA LINE-1 demethylation (defined as the largest percent decrease from baseline in methylation values within a subject between Day 8 and Day 29 of the first treatment course) using the descriptive statistics. Also, bar charts will be used to assess the maximum DNA LINE-1 demethylation within a subject between Day 8 and Day 29 of the first treatment course.
- Line plots of DNA LINE-1 demethylation will be produced for responders, non-responders, and overall in the pharmacodynamics analyses set. Responders will be defined as those subjects who meet the criteria of overall remission.

12 Rationale for Target Number of Subjects

For Cohorts 1, 2, and 4, tolerability will be evaluated in at least 3 subjects per cohort based on the Guidelines for Clinical Evaluation of Antimalignant Tumor Drugs. If DLTs are evaluated in 3 subjects in a cohort for the recommended dose and regimen, additional subjects will be enrolled for further safety evaluation in 6 subjects. For Cohort 3, tolerability will be evaluated in 6 subjects.

13 Changes From Analyses Planned in the Protocol

Categorization of urinalysis in shift tables was changed from CTCAE grade to qualitative value.

One interim analysis for cohort 1, 2 and 4 of this study will take place that the data will be locked on 25Aug2017.

Kaplan-Meier plots of overall survival with median survival time will be produced regardless of number of subjects in each cohort.

14 References

¹ Cheson BD, Bennett JM, Kopecky KJ, Büchner T, Willman CL, Estey EH, et al. Revised recommendations of the International Working Group for Diagnosis, Standardization of Response Criteria, Treatment Outcomes, and Reporting Standards for Therapeutic Trials in Acute Myeloid Leukemia. *J Clin Oncol*. 2003 Dec 15;21(24):4642-9.

² NCCN Guidelines: Acute Myeloid Leukemia. Version 2.2014. NCCN.org.
